12.7.2.3 Laboratory Data

Laboratory values will be evaluated according to the Toxicity Grading Scale for Healthy Adult and Adolescent Volunteers Enrolled in Preventive Vaccine Clinical Trials (FDA) presented in Appendix 1. Derived toxicity grades are done based only on the numeric value of the parameter assessed.

The number and percentage of participants with each toxicity grade will be tabulated by baseline and maximum post-baseline worst result for each parameter and direction of change. Shift tables of laboratory results by worst change from baseline grade will be presented for the following parameters and direction of change:

- Haematology: leukocytes (low) [WBC decrease], leukocytes (high) [WBC increase], eosinophils (high) [eosinophils], lymphocytes (low) [lymphocytes decrease], neutrophils (low) [neutrophils decrease], haemoglobin (low) [haemoglobin], platelets (low) [platelets decrease], prothrombin time (high) [prothrombin time]
- Biochemistry: alanine aminotransferase (high) [alanine aminotransferase], aspartate aminotransferase (high) [aspartate aminotransferase], alkaline phosphatase (high) [alkaline phosphatase], direct bilirubin (high) [bilirubin increase], urea nitrogen (high) [blood urea nitrogen], creatinine (high) [creatinine], potassium (low) [hypokalaemia], potassium (high) [hyperkalaemia], sodium (low) [hyponatremia], sodium (high) [hypernatremia], albumin (low) [hypoalbuminemia]

Participants with any out of range values as determined using the central lab reference ranges will be listed.

All haematology, biochemistry, urinalysis, urine dipstick, and viral measurement results will be listed separately. In addition, investigator assessed clinically significant laboratory results (haematology, biochemistry, urinalysis) will be listed.

Pregnancy test results for female participants of childbearing potential will be listed.

12.7.2.4 Vital Signs

Shift tables of worst change from baseline in each participant will be presented by parameter. Worst change is defined as the lowest and highest post-baseline toxicity grades for pulse rate (bradycardia, tachycardia) and systolic blood pressure (hypotension, hypertension), and as the highest post-baseline toxicity grades for diastolic blood pressure (hypertension) and temperature (fever). Toxicity grades are based on the Food and Drug Administration (FDA) Guidance on Toxicity Grading Scale as described in Appendix 1 of the Protocol.

All vital sign data will be included in a by-participant listing. Participants with any treatment-emergent out of range vital sign values, defined as outside of the normal range criteria specified in Table 8, will be listed separately.

Table 8 Vital Signs Normal Ranges

Vital Sign Parameter (unit)	Normal range
Pulse Rate (beats/min)	45-130 (inclusive)
Systolic Blood Pressure (mmHg)	90-140 (inclusive)
Diastolic Blood Pressure (mmHg)	< 91
Temperature (°C)	< 38.0

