**Contains Nonbinding Recommendations**

Vital Signs *	Mild (Grade 1)	Moderate(Grade 2)	Severe (Grade 3)	Potentially Life Threatening (Grade 4)
Fever (°C) ** (°F) **	38.0 – 38.4 100.4 – 101.1	38.5 – 38.9 101.2 – 102.0	39.0 – 40 102.1 – 104	> 40 > 104
Tachycardia - beats per minute	101 – 115	116 – 130	> 130	ER visit or hospitalization for arrhythmia
Bradycardia - beats per minute***	50 – 54	45 – 49	< 45	ER visit or hospitalization for arrhythmia
Hypertension (systolic) - mm Hg	141 – 150	151 – 155	> 155	ER visit or hospitalization for malignant hypertension
Hypertension (diastolic) - mm Hg	91 – 95	96 – 100	> 100	ER visit or hospitalization for malignant hypertension
Hypotension (systolic) - mm Hg	85 – 89	80 – 84	< 80	ER visit or hospitalization for hypotensive shock
Respiratory Rate – breaths per minute	17 – 20	21 – 25	> 25	Intubation

\* Subject should be at rest for all vital sign measurements.

\*\* Oral temperature, no recent hot or cold beverages or smoking.

\*\*\* When resting heart rate is between 60 – 100 beats per minute. Use clinical judgement when characterizing bradycardia among some healthy subject populations, for example, conditioned athletes.

Systemic (General)	Mild (Grade 1)	Moderate(Grade 2)	Severe (Grade 3)	Potentially Life Threatening (Grade 4)
Nausea/vomiting	No interference with activity or 1 – 2 episodes/24 hours	Some interference with activity or > 2 episodes/24 hours	Prevents daily activity, requires outpatient IV hydration	ER visit or hospitalization for hypotensive shock
Diarrhea	2 – 3 loose stools or < 400 gms/24 hours	4 – 5 stools or 400 – 800 gms/24 hours	6 or more watery stools or > 800gms/24 hours or requires outpatient IV hydration	ER visit or hospitalization
Headache	No interference with activity	Repeated use of non-narcotic pain reliever > 24 hours or some interference with activity	Significant, any use of narcotic pain reliever or prevents daily activity	ER visit or hospitalization
Fatigue	No interference with activity	Some interference with activity	Significant, prevents daily activity	ER visit or hospitalization
Myalgia	No interference with activity	Some interference with activity	Significant, prevents daily activity	ER visit or hospitalization

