12.7.1.3 Vital Signs

Vital sign values will be considered potentially clinically significant if they meet either the low or high potentially clinically significant criteria listed in Table 7. The number and percentage of participants with any potentially clinically significant post-baseline value overall and by each criteria will be tabulated.

Table 7 Criteria for Potentially Clinically Significant Vital Signs

Vital Sign Parameter (unit)	Lower Limit	Upper Limit
Pulse rate (beats per minute)	< 45	> 130
Systolic blood pressure (mmHg)	< 80	> 155
Diastolic blood pressure (mmHg)		> 100
Temperature (°C)		≥ 39.0

A graphical display of each parameter by time point will be presented similarly to laboratory data.

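### SAP 12.7.2.4 uses the Grade 3 limits as the normal range for pulse and takes the lowest toxicity grade as the worst low-side result; both are minor reporting errors that need correcting

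*SAP*

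**What the plan says.** SAP 12.7.2.4 plans two targeted vital-sign outputs besides the full by-participant listing.

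- **Out-of-range listing.** The rule is: "Participants with any treatment-emergent out of range vital sign values, defined as outside of the normal range criteria specified in Table 8, will be listed" in an output of their own. Table 8 sets pulse at "45-130 (inclusive" and systolic pressure at "90-140 (inclusive". Diastolic pressure is normal below 91 mmHg and temperature below 38.0 °C.
- **Shift tables.** The rule is: "Worst change is defined as the lowest and highest post-baseline toxicity grades for pulse rate (bradycardia, tachycardia) and systolic blood pressure (hypotension, hypertension". For diastolic pressure and temperature it is the highest grade only.

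The grading source is fixed in the same section: "Toxicity grades are based on the Food and Drug Administration (FDA) Guidance on Toxicity Grading Scale as described in Appendix 1 of the Protocol". The bradycardia row of that scale carries a footnote: "When resting heart rate is between 60 – 100 beats per minute".

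SAP 12.7.1.3 separately tabulates values that meet Table 7, titled "Criteria for Potentially Clinically Significant Vital Signs", and plots each parameter by time point. Its pulse limits are below 45 and above 130.

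**The concern.** The pulse row of Table 8 does not follow the logic of the rows beside it. A listing meant to pick out readings outside the normal range would, for pulse alone, pick out only what Table 7 already counts.

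The shift-table rule points the wrong way on the low side. On the Appendix 1 scale a lower blood pressure or a slower pulse earns a higher grade. Taking the lowest grade therefore selects the mildest reading, in a sentence that sets out to define the worst.

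Vital signs are among the primary safety endpoints. SAP 6.1 has already replaced the descriptive vital-sign summaries of the protocol with listings, so the shift table is the only planned tabulation that could show Grade 1-2 changes. A programmer who follows the text would produce a pulse listing that is too short and shift tables with too little bradycardia and hypotension.

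**Working it through.** No sample-size or error-rate formula applies. The check sets the definitions side by side and then applies the worst-change rule to example readings.

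**1. Table 8 against the grading scale.** Inputs: protocol Appendix 1 (vital signs table), SAP Table 7, SAP Table 8.

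| Parameter | Appendix 1 Grade 1 | Appendix 1 Grade 3 | Table 7 limit | Table 8 normal | Graded values called normal |
|---|---|---|---|---|---|
| Pulse, low | 50-54 | <45 | <45 | 45 and above | 45-54 |
| Pulse, high | 101-115 | >130 | >130 | up to 130 | 101-130 |
| Systolic, low | 85-89 | <80 | <80 | 90 and above | none |
| Systolic, high | 141-150 | >155 | >155 | up to 140 | none |
| Diastolic | 91-95 | >100 | >100 | <91 | none |
| Temperature (°C) | 38.0-38.4 | 39.0-40 | ≥39.0 | <38.0 | none |

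The stated pulse range reproduces exactly as everything that is not Grade 3. The systolic, diastolic and temperature ranges reproduce exactly as everything that is not graded at all.

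For pulse, the values called normal although graded are:

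- Bradycardia Grade 1 (50-54) and Grade 2 (45-49): 5 + 5 = 10 integer values.
- Tachycardia Grade 1 (101-115) and Grade 2 (116-130): 15 + 15 = 30 integer values.

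That is every Grade 1-2 pulse value. No pulse value lies outside Table 8 without also meeting Table 7. The values Appendix 1 leaves ungraded are 55-100.

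**2. The lowest-grade rule.** Take a participant with 8 post-baseline readings (Day 0 after dosing, Day 7, Day 28 before and after dosing, Day 35, Months 3, 6 and 9).

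- Pulse 62, 44, 64, 63, 61, 66, 65, 64 gives bradycardia grades 0, 3, 0, 0, 0, 0, 0, 0. The lowest is 0 and the highest is 3.
- Systolic 112, 78, 118, 115, 120, 116, 119, 117 gives hypotension grades 0, 3, 0, 0, 0, 0, 0, 0. The lowest is 0 and the highest is 3.

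The lowest grade exceeds 0 only if all readings are graded. As an illustration, assume the 8 readings are independent and each is graded with probability p. The documents give no value for p, so a range is shown. The chance that all are graded is p^8:

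| p | p^8 |
|---|---|
| 0.1 | 0.00000001 |
| 0.3 | 0.00007 |
| 0.5 | 0.004 |
| 0.8 | 0.17 |

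Readings within one person are correlated, so persistent bradycardia or hypotension would show more often than this. Pulse readings of 50, 48, 52, 47, 51, 53, 49, 50 have a lowest grade of 1 (highest 2).

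**3. What reaches which output, with the text followed literally.**

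| Finding | Table 7 | Table 8 listing | Shift table | Full listing and plots |
|---|---|---|---|---|
| Tachycardia Grade 1-2 | no | no | yes | yes |
| Bradycardia Grade 1-2 | no | no | no* | yes |
| Bradycardia Grade 3 | yes | yes | no* | yes |
| Hypotension Grade 1-2 | no | yes | no* | yes |
| Hypotension Grade 3 | yes | yes | no* | yes |

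*Unless every post-baseline reading is graded; the table then shows the mildest of the grades.

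**4. The rest of the SAP.** SAP 6.1 bases vital-sign shift tables on the worst result after baseline. SAP 12.7.2.3 tabulates laboratory grades at their post-baseline maximum, separately by direction of change. The lowest-grade wording agrees with neither.

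**The case against.** The strongest case against is that little is lost and the intent is clear.

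- **Nothing disappears from the report.** All vital signs are listed by participant and plotted, and Grade 1-2 tachycardia enters the shift table through the highest grade. A systolic reading of 78 mmHg is counted in Table 7 and listed under Table 8. This stands. A reader might infer that bradycardia and hypotension would vanish from the results; the documents do not support that.
- **The literal reading is not the only one.** The sentence defines worst change and pairs lowest and highest with low- and high-direction conditions, so the authors probably meant the lowest and highest measured values, or grades in each direction. SAP 6.1 points the same way. This stands as to intent, but the text says grade, and a rule that is right only when read against its wording should be reworded.
- **Myocarditis and thyroid disease are events of special interest, so a reader might infer that their detection suffers.** It does not: SAP 10.5.4 has the investigator identify these events, and nothing ties that to Table 8.
- **Neither document requires Table 8 to match the ungraded range.** Protocol 10.2.2.6.3 asks for out-of-range listings without giving numbers, and the bradycardia footnote means that 45-54 beats/min is not graded in every participant. This stands in part. The 10 low-side values are an upper bound, and 55-100 is an inference from the other rows. But the SAP gives no reason to treat pulse differently, and the high-side mismatch (101-130) does not depend on the footnote.

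**Conclusion.** Both rules are wrong as written, and the consequence is limited to reporting. For pulse, the out-of-range listing adds nothing to Table 7 and flags no Grade 1-2 value (45-54 and 101-130 beats/min). In the shift tables, low-side changes in pulse and systolic pressure are understated, with Grade 0 shown for any participant who has at least one ungraded reading after baseline. The one category without any targeted output is Grade 1-2 bradycardia.

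The shift-table conclusion rests on the literal wording; if the programmers already take the highest grade in each direction, only the text needs repair. The pulse-range conclusion rests on Table 8 being meant to follow one principle for all four parameters, which the other three rows bear out. Neither error alters the Table 7 counts, the adverse event summaries or the identification of events of special interest. This is a minor reporting correction.

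**What to change.** In SAP 12.7.2.4:

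1. Change the Table 8 pulse range to 55-100 beats/min inclusive, the values Appendix 1 leaves ungraded. Add the Appendix 1 footnote that bradycardia grading applies when the resting heart rate is 60-100.
2. Define worst change as the highest post-baseline toxicity grade, taken separately in the low direction (bradycardia, hypotension) and the high direction (tachycardia, hypertension, fever). This matches the laboratory rule in 12.7.2.3.

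The cost is one table cell with its footnote and one sentence, plus the matching programming. The downside is a longer out-of-range listing for pulse. These are reporting definitions only; no clinical rule is affected.

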12.7.2.5 Physical Examinations

All physical examination data with corresponding clinical significance will be listed only.

14.0 Important Protocol Deviation Identification Listings

Not applicable.

15.0 Glossary of Abbreviations

Glossary of Abbreviations:	
AE	Adverse event
AESI	Adverse Event of Special Interest
ALT	Alanine Aminotransferase
AST	Aspartate Aminotransferase
ChAdOx1	Chimpanzee Adenovirus Oxford 1
CHB	Chronic Hepatitis B Virus
CRF	Case Report Form
DMC	Data Monitoring Committee
DNA	Deoxyribonucleic Acid
eCRF	Electronic Case Report Form
ELISpot	Enzyme-linked Immunosorbent Spot
FDA	Food and Drug Administration
GM	Geometric Mean
GSD	Geometric Standard Deviation
HBcAb	Hepatitis B Core-related Antibody
HBcrAg	Hepatitis B Core-related Antigen
HBeAg	Hepatitis B e-Antigen
HBpgRNA	Hepatitis B Pregenomic RNA
HBsAb	Hepatitis B Surface Antibody
HBsAg	Hepatitis B Surface Antigen
HBV	Hepatitis B Virus
ICS	Intracellular Cytokine Staining
IXRS	Interactive Voice/Web Response System
LFTs	Liver Function Tests
LLoQ	Lower Limit of Quantification
MedDRA	Medical Dictionary for Regulatory Activities
MVA	Modified Vaccinia Virus Ankara
PBMC	Peripheral Blood Mononuclear Cell
Pfu	Plaque Forming Units
PT	Preferred Term
RNA	Ribonucleic Acid
SAE	Serious Adverse Event

SAP	Statistical Analysis Plan
SAS	Statistical Analysis Software
SFU	Spot-forming Unit
SI	Standard International
SMC	Safety Monitoring Committee
TEAE	Treatment Emergent Adverse Event
ULN	Upper Limit of Normal
Vp	Viral Particles

16.0 List of DMC and Interim Analysis Outputs

TFL	DMC	Interim
Table 14.1.1.3 Participant Disposition	✓	✓
Table 14.1.2.1 Demographic Characteristics	✓	✓
Table 14.2.1 Summary of HBsAg Geometric Mean by Time Point	✓	✓
Table 14.3.1.1 Summary of Exposure	✓	✓
Table 14.3.2.2 Treatment-Emergent Adverse Events by System Organ Class and Preferred Term	✓	✓
Table 14.3.2.13 Grade 3 or Greater Treatment-Emergent Adverse Events Related to Study Vaccines by System Organ Class and Preferred Term	✓	✓
Table 14.3.2.14 Grade 3 or Greater Treatment-Emergent Adverse Events Related to Nivolumab by System Organ Class and Preferred Term	✓	✓
Table 14.3.2.16 Participants with Treatment-Emergent Adverse Events with Outcome of Death	✓	✓
Table 14.3.2.17 Serious Treatment-Emergent Adverse Events by System Organ Class and Preferred Term	✓	✓
Table 14.3.2.18 Participants Who Experienced Serious Treatment-Emergent Adverse Events	✓	✓
Table 14.3.2.25 Participants Who Experienced Treatment-Emergent Adverse Events Leading to Discontinuation of Study Vaccines or Nivolumab	✓	✓
Table 14.3.2.27.a Solicited Adverse Events by Intensity Grade after each Vaccination	✓	✓
Table 14.3.2.27.b Solicited Adverse Events by Intensity Grade after each Vaccination – Sensitivity Analysis including all data	✓	✓
Table 14.3.2.28 Local and Systemic Reactogenicity by Vaccination and Time Point	✓	✓
Table 14.3.3.1.1 Potentially clinically significant Post-baseline Laboratory Results	✓	✓
Table 14.3.3.2.3 Participants With an Out of Range Haematology Result	✓	✓
Table 14.3.3.3.3 Participants With an Out of Range Biochemistry Result	✓	✓
Table 14.3.4.1 Potentially Clinically Significant Vital Sign Results	✓	
Listing 16.2.1.2 End of Study	✓	✓
Listing 16.2.1.3 End of Treatment	✓	✓
Listing 16.2.7.1 Treatment-Emergent Adverse Events	✓	✓
Listing 16.2.7.2 Solicited Adverse Events (eDiary)	✓	✓
Listing 16.2.7.3 Local and Systemic Reactogenicity	✓	✓

Appendix 1. Tables for Laboratory Abnormalities

Serum*	Mild (Grade 1)	Moderate (Grade 2)	Severe (Grade 3)	Potentially Life Threatening (Grade 4)
Hyponatremia (mEq/L)	132 - 134	130 - 131	125 - 129	
Hypernatremia (mEq/L)	144 - 145	146 - 147	148 - 150	---
Hypokalemia (mEq/L)	3.5 – 3.6	3.3 – 3.4	3.1 – 3.2	---
Hyperkalemia (mEq/L)	5.1 – 5.2	5.3 – 5.4	5.5 – 5.6	---
Blood Urea Nitrogen (mg/dL)	23 - 26	27 - 31	>31	---
Creatinine (mg/dL)	1.5 – 1.7	1.8 – 2.0	2.1 – 2.5	>2.5
Hypoalbuminemia (g/dL)	2.8 – 3.1	2.5 – 2.7	<2.5	---
Alanine Aminotransferase (U/L)	1.1 – 2.5 x ULN	>2.5 – 5.0 x ULN	>5.0 – 10.0 x ULN	>10.0 x ULN
Aspartate Aminotransferase (U/L)	1.1 – 2.5 x ULN	>2.5 – 5.0 x ULN	>5.0 – 10.0 x ULN	>10.0 x ULN
Alkaline Phosphatase (U/L)	1.1 – 2.0 x ULN	>2.0 – 3.0 x ULN	>3.0 – 10.0 x ULN	>10.0 x ULN
Bilirubin Increase (mg/dL) – when accompanied by any increase in LFT; increase by factor	1.1 – 1.25 x ULN	>1.25 – 1.5 x ULN	>1.5 – 1.75 x ULN	>1.75 x ULN
Bilirubin Increase (mg/dL) - when LFT is normal; increase by factor	1.1 – 1.5 x ULN	>1.5 – 2.0 x ULN	>2.0 – 3.0 x ULN	>3.0 x ULN

* The laboratory values provided in the tables serve as guidelines and are dependent upon institutional normal parameters. Institutional normal reference ranges should be provided to demonstrate that they are appropriate.

ULN is the upper limit of the normal range.

Haematology*	Mild (Grade 1)	Moderate (Grade 2)	Severe (Grade 3)	Potentially Life Threatening (Grade 4)
Haemoglobin [Female] (g/dL)	11.0 – 12.0	9.5 – 10.9	8.0 – 9.4	<8.0
Haemoglobin [Female] Decrease from Baseline Value (g/dL)	>0 – 1.5	1.6 – 2.0	2.1 – 5.0	>5.0
Haemoglobin [Male] (g/dL)	12.5 – 13.5	10.5 – 12.4	8.5 – 10.4	<8.5
Haemoglobin [Male] Decrease from Baseline Value (g/dL)	>0 – 1.5	1.6 – 2.0	2.1 – 5.0	>5.0
WBC Decrease ($10^3/uL$)	2.500 – 3.500	1.500 – 2.499	1.000 – 1.499	<1.000
WBC Increase ($10^3/uL$)	10.800 – 15.000	15.001 – 20.000	20.001 – 25.000	>25.000
Lymphocytes Decrease ($10^3/uL$)	0.750 – 1.000	0.500 – 0.749	0.250 – 0.499	<0.250
Neutrophils Decrease ($10^3/uL$)	1.500 – 2.000	1.000 – 1.499	0.500 – 0.999	<0.500
Eosinophils ($10^3/uL$)	0.650 – 1.500	1.501 – 5.000	>5.000	—
Platelets Decrease ($10^3/uL$)	125.000 – 140.000	100.000 – 124.000	25.000 – 99.000	<25.000
Prothrombin Time (sec)	1.0 – 1.10 x ULN	>1.10 – 1.20 x ULN	>1.20 – 1.25 x ULN	>1.25 x ULN

* The laboratory values provided in the tables serve as guidelines and are dependent upon institutional normal parameters. Institutional normal reference ranges should be provided to demonstrate that they are appropriate.

ULN is the upper limit of the normal range.

Urine*	Mild (Grade 1)	Moderate (Grade 2)	Severe (Grade 3)	Potentially Life Threatening (Grade 4)
Urine Erythrocytes (rbc/hbf)	1 – 10	11 – 50	>50	---
Urine Glucose	Trace	+	++	---
Urine Protein	Trace	+	++	---

* The laboratory values provided in the tables serve as guidelines and are dependent upon institutional normal parameters. Institutional normal reference ranges should be provided to demonstrate that they are appropriate.
